#### **Cohort B: 40 Subjects**

Once enrollment in Cohort A is complete, then enrollment into Cohort B will begin.

1. 40 Subjects that have recently undergone either a standard "in the sleep-lab" diagnostic polysomnography (per standard of care medical guidelines, and not for research purposes) or an "at home" PSG test and have been diagnosed with OSA will be recruited into the research study where we will assess the beneficial effects of oxytocin treatment.
2. For research: These 40 subjects will undergo an "in the sleep-lab" diagnostic polysomnography that would be identical to the one they had for standard of care medical guidelines if they were diagnosed with OSA "in the sleep-lab". This research

polysomnography should be performed within **4 weeks** of their OSA diagnosis PSG. This PSG that is being performed for research will be funded externally by the investigating group.

*If subjects are female and of child bearing potential, then their birth control method for the duration of the study will be recorded, and a urine pregnancy test will be performed prior to the PSG.*

3. Subjects will be randomized by the Investigational Drug Services Pharmacy of the MFA to be administered either Oxytocin (40 IU) or placebo within one hour prior to beginning the study polysomnography.
  - a. Both the polysomnography technician, the patient, and all research staff will be blinded to this randomization. The only un-blinded personnel will be the IDS pharmacy staff.
4. Subjects will then return within **4 weeks** to have a **second research study** polysomnography performed by the sleep-lab. This polysomnography that is being performed for research will be funded externally by the investigating group.
5. Subjects will be administered the intervention that *they did not receive* during the first research PSG study within one hour prior to beginning the second polysomnography. Either Oxytocin (40 IU) or placebo.
  - a. Both the polysomnography technician, the patient, and all research staff will be blinded to this randomization. The only un-blinded personnel will be the IDS pharmacy staff.

*For example: If at study polysomnography 1 a subject is randomized to receive placebo 1 hour prior to the start of the polysomnography, then at study polysomnography 2 the subject will be administered oxytocin (40 IU) 1 hour prior to the start of the polysomnography.*

6. The following 4 outcome measurements will be compared between the two sequential diagnostic PSGs (initial standard of care without oxytocin, and second for research with oxytocin) in the same subjects:
  - i. basal heart rate before sleep (primary outcome)
  - ii. mean changes in heart rate with apneic and hypopneic events (primary outcome)
  - iii. apnea-hypopnea index (secondary outcome)
  - iv. percentage of time spent by the patient with oxygen saturations: > 90%, > 80% but < 90%, and < 80% (secondary outcome)

The intranasal oxytocin dose is 40 IU. The drug will be stored in the Investigational Drug Pharmacy according to the vendor's recommendations.

Polysomnography (PSG) is a comprehensive recording of the biophysiological changes that occur during sleep. It is usually performed at night, when most people sleep, though some labs can accommodate shift workers and people with circadian rhythm sleep disorders and do the test at other times of the day. The PSG monitors many body functions including brain (EEG), eye movements (EOG), muscle activity or skeletal muscle activation (EMG) and heart rhythm (ECG) during sleep. After the identification of the sleep disorder sleep apnea in the 1970s, respiratory airflow and respiratory effort indicators were added, along with peripheral pulse oximetry.

Inclusion Criteria:

- Men or women 18 years old or older of any ethnic background

- Subjects that have recently undergone a standard "in the sleep-lab" diagnostic polysomnography (per standard of care medical guidelines), or the "at home" diagnostic test for cohort B, and have been diagnosed with OSA will be recruited into a follow-up study to assess the beneficial effects of oxytocin treatment.

Exclusion Criteria:

- Pregnant or nursing women.
- Women at any child bearing age who are not willing to undergo pregnancy tests, and stable and reliable methods to prevent pregnancy
  - A female subject of childbearing potential is a non-menopausal female who has not had a hysterectomy, bilateral oophorectomy, or medically documented ovarian failure. Menopause can be assumed to have occurred in a woman when there is either:
    1. Appropriate medical documentation of prior complete bilateral oophorectomy  
OR
    2. Permanent cessation of previously occurring menses as a result of ovarian failure with documentation of hormonal deficiency. Ovarian hormonal deficiency is documented by serum follicle stimulating hormone (FSH) level elevated to within the post-menopausal range based on the laboratory reference range where the hormonal assay is performed.  
OR
    3. Menopause is defined as occurring 12 months after your last menstrual period and marks the end of menstrual cycles
- Subjects who are on medications that affect cardiac autonomic function (eg. Beta blockers)
- Smokers
- Subjects who are unable to read or answer questions in the English language

The following information will be recorded on each patient before and after the use of intranasal oxytocin:

- Clinical data:
  1. Demographics — Age, gender, ethnicity, weight, BMI.
  2. Physiological data to be acquired:
    - a. Basal heart rate before sleep
    - b. Apnea-hypopnea index
    - c. Mean changes in heart rate with apneic and hypopneic events
    - d. Percentage of time spent by the patient with oxygen saturations: > 90%, > 80% but < 90%, and < 80%.
  3. Medical History Information: Current and past medical conditions, to be investigated for correlations to sleep.
  4. Standard of care sleep study data:
- The Polysomnography (PSG) monitors many body functions during sleep, including brain (EEG), eye movements (EGG), muscle activity or skeletal muscle activation (EMG), heart rhythm (ECG), respiratory airflow, thoracic and abdominal respiratory effort, body position, limb movement, and oxygen saturation using pulse oximetry. Recording and scoring is done per the standards set by the American Academy of Sleep Medicine.

All these data will be stored in a secured cabinet in the division of Pulmonary, Critical Care and Sleep Disorders offices. The primary investigator and study staff only will have access to these data. These data will lack any information that may lead to identifying any subject in the research.

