**Background:**

One major, yet poorly understood cardiovascular health risk that occurs in as many as 24% of males and 9% of females within the US population is obstructive sleep apnea (OSA). Severe OSA increases cardiovascular mortality 4 fold, and even when corrected for other risk factors increases cardiovascular mortality 3 fold. OSA can participate in both the initiation and progression of several cardiovascular diseases including sudden death, hypertension, arrhythmias, myocardial ischemia and stroke. Treatment of OSA is primarily continuous positive airway pressure (CPAP).

Diminished cardiac vagal activity is thought to be associated with many of the adverse cardiovascular consequences of OSA. Heart rate is dominated by cardioinhibitory parasympathetic activity. Parasympathetic cardiac vagal activity is typically cardioprotective and there is a high tonic level of parasympathetic and little sympathetic cardiac activity at rest. Re-establishment of cardiac vagal activity prevents arrhythmias, decreases risk of sudden death, and protects against ischemic/reperfusion injury, suggesting that restoring parasympathetic cardiac activity could be an effective therapeutic target to decrease mortality and morbidity associated with OSA.

In human volunteers intranasal administration of oxytocin significantly increases parasympathetic and decreases sympathetic cardiac control. In addition to the classic effects of oxytocin on uterine contraction and milk ejection, recent work indicates oxytocin is present in both males and females and has an important role in both behavior and cardiovascular homeostasis, particularly during anxiety and stress.

There are no clinical guidelines for the use of intranasal oxytocin in the treatment of sleep apnea but we propose that it may have a positive impact on the outcome of patients with sleep apnea, however, this research is not intended to change any clinical guidelines.

This project's specific aim will test the following hypothesis:

Intranasal oxytocin administration will blunt the deleterious hypoxia/hypercapnia induced changes in heart rate that occur during apnea in patients with OSA.

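### Cohort B mixes home- and lab-diagnosed subjects but specifies neither sequence balance by diagnostic route nor period and route terms, so any first-lab-night effect can shift the oxytocin contrast by chance

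*Combined protocol and SAP*

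**What the plan says.** All references are to the combined protocol and SAP.

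- **Recruitment.** Cohort B item 1 admits subjects with a standard in-lab diagnostic polysomnography (PSG) "or an 'at home' PSG test and have been diagnosed with OSA will be recruited into the research study". The inclusion criteria repeat the second route: "or the 'at home' diagnostic test for cohort B, and have been diagnosed with OSA". The expected share of each route is not given.
- **Setting of the first research night.** Item 2 puts it in the sleep-lab and describes a study "that would be identical to the one they had for standard of care medical guidelines if they were diagnosed with OSA" in the lab. The match to the diagnostic night is therefore claimed only for the lab-diagnosed.
- **Allocation.** Item 3: "Subjects will be randomized by the Investigational Drug Services Pharmacy of the MFA to be administered either Oxytocin (40 IU) or placebo". Items 4 and 5 bring each subject back within 4 weeks for the other intervention, and the worked example confirms a two-period crossover. Allocation ratio, blocks, strata and the method of generating the sequence are not stated.
- **Analysis.** Statistical Considerations names ANOVA and Fisher's exact test for repeated measures. It names no period, sequence or diagnostic-route term.
- **Comparison.** Item 6 sets the standard-of-care night without oxytocin against the research night with oxytocin. That is not the oxytocin-placebo contrast that items 3 to 5 create.

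**The concern.** Lab-diagnosed subjects have already slept in a sleep-lab. For a home-tested subject, research night 1 may be the first time. An unfamiliar setting could plausibly change pre-sleep heart rate, which is a primary outcome, so the home-tested could show a night 1 to night 2 difference that the lab-diagnosed do not.

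In a crossover such a difference cancels if equal numbers of home-tested subjects take each sequence. If more of them start on oxytocin than on placebo, or the reverse, part of it enters the treatment contrast. Nothing in the design text secures that balance, and nothing in the analysis text adjusts for its absence. The mix of routes matters because an ordinary period term assumes one night effect for everyone. When only some subjects carry the effect, that term does not fully remove it.

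**Working it through.** The documents give no power, SD, effect size or rationale for the 40, so there is no planned figure to reproduce.

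**Inputs**
- From the documents: 40 subjects, two research nights, two diagnostic routes.
- Assumed: simple 1:1 randomisation; 20 home-tested subjects (10 and 40 as the range); delta of 2, 4 or 6 bpm in home-tested subjects and zero in the others; two-sided 5% test.

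**Model.** Let D be a subject's oxytocin night minus placebo night, with true effect tau. A home-tested subject has mean D = tau + delta if oxytocin comes first and tau - delta if placebo comes first. A lab-tested subject has mean D = tau. Let h1 and h2 be the home-tested subjects in the two sequences, and n1 and n2 all subjects in each.

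**Bias given the split**
- Unadjusted paired mean: delta x (h1 - h2)/40.
- With a period term: (delta/2) x (h1/n1 - h2/n2).
- With period and period-by-route terms: 0.

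**Size of the shift, unadjusted.** Under simple randomisation h1 - h2 has mean 0 and SD equal to the square root of the number home-tested.

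| Home-tested (assumed) | SD of h1 - h2 | SD of shift | delta 2 bpm | 4 bpm | 6 bpm |
|---|---|---|---|---|---|
| 10 | 3.16 | 0.079 x delta | 0.16 | 0.32 | 0.47 |
| 20 | 4.47 | 0.112 x delta | 0.22 | 0.45 | 0.67 |
| 40 | 6.32 | 0.158 x delta | 0.32 | 0.63 | 0.95 |

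The last row also covers an equal night effect in both routes. An ordinary period term removes that case.

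**Unlucky splits, 20 home-tested (exact binomial).** A split of 14:6 or worse has probability 0.115 and shifts the mean by at least 8/40 = 0.20 x delta. A split of 15:5 or worse has probability 0.041 and shifts it by at least 10/40 = 0.25 x delta.

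**When a period term is not enough.** With 20 subjects per sequence overall but the home-tested split 14:6, the period-adjusted bias is (delta/2) x (14/20 - 6/20) = 0.20 x delta, the same as unadjusted.

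**Simulation.** 6,000 runs per scenario, tau = 0, SD of D set to 1, 20 home-tested, delta = 1 SD.

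| Quantity | Unadjusted | Period | Period and period-by-route |
|---|---|---|---|
| Simple randomisation: type I error | 0.051 | 0.050 | 0.053 |
| Simple randomisation: SD of estimate | 0.194 | 0.180 | 0.163 |
| Simple randomisation, split 14:6 or worse: type I error | 0.164 | 0.093 | 0.047 |
| Stratified by route: type I error | 0.016 | 0.028 | 0.051 |
| Stratified by route: SD of estimate | 0.158 | 0.158 | 0.158 |

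The mean estimate was within 0.005 of zero throughout. The unadjusted SD agrees with theory: sqrt(1/40 + 0.112^2) = sqrt(0.025 + 0.0125) = 0.194. The conditional 0.164 rests on about 12% of runs, some 720, so its Monte Carlo standard error is sqrt(0.164 x 0.836/720) = 0.014; a separate simulation gave 0.17 to 0.19. At delta = 0.5 SD the conditional figures are 0.089, 0.055 and 0.045.

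**The case against.** Much of the case on the other side stands.

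- **Silence is not a method.** A reader might infer that sequence is randomised without balance or strata. The text names only who randomises; a blocked or stratified list would be compatible with it. Every imbalance probability above is conditional on simple randomisation.
- **No systematic false effect.** A reader might infer that the first lab night turns into an apparent oxytocin effect. Each subject is their own control and order is random, so the expected shift is zero and the overall error rate is nominal. Inflation appears only given a poor split.
- **Mixing is not the root cause.** In an unadjusted analysis an all-home cohort would have a larger shift. Mixing matters because it defeats the ordinary period term.
- **The premise is assumed.** The documents mention no first-night effect, and give neither its size nor the home-tested share.
- **Balance is not a cure whatever the analysis.** Without the model terms a stratified test is conservative, and with them the bias goes even under simple randomisation. Balanced sequences do nothing for item 6 as written.
- **The Background remark on oxytocin does not help.** That it "has an important role in both behavior and cardiovascular homeostasis, particularly during anxiety and stress" would suggest that its effect differs between nights. That is a treatment-by-night interaction, which balancing sequence does not remove and which is not what is computed here.
- **The study is exploratory**, meant to give preliminary data, which limits how much machinery it needs.

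What remains is that neither the design remedy nor the analysis remedy is written down. Zero bias on average is limited comfort when the trial is randomised once and reported with the split it happened to get.

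**Conclusion.** The point holds as one of conditional bias and lost precision. With 20 home-tested subjects, simple randomisation and a first-lab-night effect of 1 SD, all assumed, the SD of the unadjusted estimate is 0.194, against 0.158 when sequence is stratified by route. Type I error is about 0.16 to 0.19 given a split of 14:6 or worse, which has probability 0.115, but about 0.05 overall. In heart-rate terms a typical shift is about a tenth of the night effect. Whether that is large relative to the standard error in bpm cannot be judged, because the documents give no SD. If no first-lab-night effect exists, the shift is zero.

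The mismatch between item 6 and the crossover is the larger related problem. Comparing the diagnostic night with the oxytocin night would make the home-versus-lab difference systematic in home-tested subjects, and randomised sequence would not protect against it.

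**What to change.** 1. **Cohort B item 3.** Have the pharmacy randomise to sequence (oxytocin then placebo, or placebo then oxytocin) 1:1, in permuted blocks of concealed, varying size, stratified by diagnostic route. State how the list is generated, and record the route.
2. **Statistical Considerations.** Prespecify the within-subject oxytocin versus placebo comparison with period and period-by-route terms. If only one change can be made, make this one: it removes the bias under the model above, and without it the stratified test is conservative.
3. **Cohort B item 6.** Reconcile the stated comparison with the crossover in items 3 to 5.

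**Cost.** One more randomisation list at the same pharmacy, with route already known at enrolment, and two model degrees of freedom (39 to 37 for 40 complete pairs). Incomplete blocks or dropouts may leave a small residual imbalance, which the model terms absorb.

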#### **Cohort A: 10 Subjects**

1. 10 subjects that have recently undergone a standard "in the sleep-lab" diagnostic polysomnography (per standard of care medical guidelines, and not for research purposes) and have been diagnosed with OSA will be recruited into the research study to assess the beneficial effects of oxytocin treatment.
2. For research: These 10 subjects will undergo another "in the sleep-lab" diagnostic polysomnography that is identical to the one that they had for standard of care to diagnose OSA. This polysomnography that is performed for research will be funded externally by the investigating group.

*If subjects are female and of child bearing potential, then their birth control method for the duration of the study will be recorded, and a urine pregnancy test will be performed prior to the PSG.*

3. Within one hour prior to the research polysomnography the subjects will be given oxytocin 40 International Units, (IU) intranasally.
4. The following 4 outcome measurements will be compared between the two sequential diagnostic polysomnographies (initial without, and second with oxytocin) in the same subjects:
  - i. basal heart rate before sleep (primary outcome)
  - ii. mean changes in heart rate with apneic and hypopneic events (primary outcome)
  - iii. apnea-hypopnea index (secondary outcome)
  - iv. percentage of time spent by the patient with oxygen saturations: > 90%, > 80% but < 90%, and < 80% (secondary outcome)

The intranasal oxytocin dose is 40 IU. The drug will be stored in the Investigational Drug Pharmacy according to the vendor's recommendations.

Polysomnography (PSG) is a comprehensive recording of the biophysiological changes that occur during sleep. It is usually performed at night, when most people sleep, though some labs can accommodate shift workers and people with circadian rhythm sleep disorders and do the test at other times of the day. The PSG monitors many body functions including brain (EEG), eye movements (EOG), muscle activity or skeletal muscle activation (EMG) and heart rhythm (ECG) during sleep. After the identification of the sleep disorder sleep apnea in the 1970s, respiratory airflow and respiratory effort indicators were added, along with peripheral pulse oximetry.

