#### **Study Treatment:**

The study medication, oxytocin, and its matching placebo will be purchased from Victoria Pharmacy in Switzerland and shipped to the MFA Investigational Drug Pharmacy via DHL Express or another express transportation service. Victoria Pharmacy will handle the packaging and shipping in accordance with the appropriate method required for the drug. The study medication will be received by and stored in the Investigational Drug Pharmacy and dispensing of study medication will be performed by a pharmacist in the Investigational Drug Pharmacy. The study is operating under FDA approved IND#120989. Patients will be administered oxytocin, 40 IU, or placebo (also a spray to be administered intranasal) within 1 hour prior to sleeping during the second sleep study. The PI will instruct the patient on how to use the spray, including how to prime the spray, and how to administer it.

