#### **Benefits/Risks:**

There are no social/cultural, financial or legal risks to the subjects from participation in this study. No additional costs will be incurred to the patient or the institution as a result of this study.

Oxytocin nasal spray is relatively safe when used as directed. Side effects are extremely rare. The intranasal oxytocin dose is 40 IU. The oxytocin and placebo sprays will be compounded by Foer's Pharmacy in Bethesda, Maryland, and then shipped to our research pharmacy, Investigational Drug Services (IDS) Pharmacy, when it is prepared. IDS will store the oxytocin and placebo sprays according to the vendor's recommendations.

Some minor side effects may include: nasal irritation, runny nose, or tearing of the eyes, nausea and vomiting and an irregular heartbeat. Intranasal oxytocin is not FDA approved. Women of childbearing age who are not on a stable, reliable form of birth control will be excluded from the study.

It is acknowledged that there may be slight emotional discomfort associated with completing the consent form and participating in the research, but subjects are always free to drop out of the study if they encounter emotional discomfort.

In animal models of social stressors oxytocin has been shown to be protective against behavioral and cardiac dysfunction. For example social isolation, which increases heart rate, diminishes HR variability and vagal regulation of the heart, was prevented with oxytocin administration. Most pertinent to the hypotheses put forth in this proposal, the stress and increased anxiety in response to inhalation of 7.5% CO2 in healthy volunteers was prevented by intranasally administered oxytocin.

In addition, in human subjects, the evidence shows that intranasal oxytocin: (1) produces no detectable subjective changes in recipients, (2) produces no reliable side-effects, and (3) is not associated with adverse outcomes when delivered in doses of 18-40 IU for short term use in controlled research settings [ref 1]

Any data containing patient identifiers will be kept in separate files from the clinical data collected and will be stored in a secure location in the Division of Pulmonary, Critical Care and Sleep Medicine.

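### Cohort B schedules one urine pregnancy test, tied to the first research PSG, and none before the second dose up to 4 weeks later, which is the only oxytocin dose for placebo-first women

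*Combined protocol and SAP*

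**What the plan says.** In Cohort B, item 2 describes the first research PSG. An unnumbered note directly after it says that, for women of child-bearing potential, the birth control method is recorded and "a urine pregnancy test will be performed prior to the PSG". Item 3 covers randomization and the first dose. Item 4 brings subjects back for a second research PSG within 4 weeks. Item 5 gives the treatment not received "during the first research PSG study within one hour prior to beginning the second polysomnography. Either Oxytocin (40 IU) or placebo". Neither item 4 nor item 5 mentions a pregnancy test.

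The worked example after item 5 describes a subject given placebo first: "then at study polysomnography 2 the subject will be administered oxytocin (40 IU) 1 hour prior to the start of the polysomnography". On blinding, items 3a and 5a both state: "The only un-blinded personnel will be the IDS pharmacy staff".

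Cohort A carries the same test sentence, word for word, but has a single research PSG and a single dose: "Within one hour prior to the research polysomnography the subjects will be given oxytocin 40 International Units".

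The related safeguards are these. Pregnant or nursing women are excluded. The Exclusion Criteria also bar "Women at any child bearing age who are not willing to undergo pregnancy tests, and stable and reliable methods to prevent pregnancy". Benefits/Risks adds: "Women of childbearing age who are not on a stable, reliable form of birth control will be excluded from the study".

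**The concern.** The test sentence fits Cohort A, where one test precedes one dose. Cohort B adds a second dosing night, and the sentence was not extended to cover it. Study Treatment also still describes one dosing night, "within 1 hour prior to sleeping during the second sleep study". That line concerns dosing and does not show how many tests were planned, but it is consistent with single-dose text carried over.

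For placebo-first women the effect is the wrong way round: the scheduled test precedes the placebo night, and the oxytocin night has none. Pregnancy is an exclusion, and the Background section lists uterine contraction among oxytocin's classic effects, so the exclusion should be confirmed at the dose that matters. Research staff are blinded to sequence and cannot retest only the women who are due for oxytocin. The rule therefore has to cover every woman of child-bearing potential at both visits.

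**Working it through.** **Schedule count, from the Cohort B section**

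| Step | Item | Dose | Pregnancy test scheduled |
|---|---|---|---|
| First research PSG | 2 and 3 | oxytocin or placebo | one, stated after item 2 |
| Second research PSG, within 4 weeks | 4 and 5 | the other treatment | none |

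Two dosing visits, one scheduled test, and none before the second dose. No other section sets a number or timing of tests. If the test is done on the day of the first PSG, it is up to 4 × 7 = 28 days old at the second dose. It can be older, because the sentence does not say same day.

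**Size of the risk**

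The plan gives no figure to reproduce. The 28-day gap and the 40 subjects come from the protocol. The other inputs are assumptions:
- allocation 1:1 (no ratio is stated);
- 4 to 10 of the 40 subjects are women of child-bearing potential;
- annual pregnancy rate a on the required contraception between 0.5% and 6%.

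1. Expected placebo-first women of child-bearing potential: 4/2 = 2 to 10/2 = 5.
2. Chance that one woman conceives in the maximum gap, 1 − (1 − a)^(28/365):
   - a = 0.5%: 1 − 0.995^(28/365) = 0.038%
   - a = 6%: 1 − 0.94^(28/365) = 0.474%
3. Chance that at least one placebo-first woman does:
   - low end: 1 − (1 − 0.00038)^2 = 0.08%
   - high end: 1 − (1 − 0.00474)^5 = 2.3%

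The high end combines the largest number of women, the highest rate and the full gap for everyone. Shorter gaps give less.

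**Cost to the analysis of a positive test on night 2**

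- Expected crossover pairs lost, counting both sequences and supposing every conception in the gap is detected: 4 × 0.00038 = 0.002 to 10 × 0.00474 = 0.05.
- If one pair is lost, the standard error of the paired difference rises by the factor √(40/39) = 1.013, or 1.3%.

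**The case against.** The strongest case is that the sentence is ambiguous and does not fix the count at one. It never names the first PSG. It sits in an unnumbered note that also covers birth control for the whole study, so it could be meant as a standing rule for each research PSG. The plural in the exclusion criterion, "Women at any child bearing age who are not willing to undergo pregnancy tests, and stable and reliable methods to prevent pregnancy", points the same way. The consent pages are not available and may describe repeat testing. On this view the protocol is merely unclear.

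Repeat testing may indeed have been intended, and it is not certain that women would go untested in practice. But the sentence is singular and follows directly on the description of the first research PSG. The plural belongs to a willingness criterion with no number or timing, and may only reflect that its subject is plural. Neither text schedules a second test, and a check before dosing should not depend on a generous reading.

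The second argument is low risk. Contraception is required, harm from one 40 IU intranasal dose in very early pregnancy is not shown in the documents, and any conception within 28 days is early enough that a urine test might miss it. These points stand as limits on size. The 0.08% to 2.3% is a conception risk over the longest gap, not the risk averted, which is lower and cannot be estimated from the documents. Against this, contraception does not detect a pregnancy, and the protocol already requires a test on top of it for the first night. The same reasoning applies to the second.

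**Conclusion.** The concern holds. As written, Cohort B has no pregnancy test before the second dose, and for placebo-first women that is the only oxytocin dose. This follows from the text and needs no assumption.

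The size does depend on the assumptions listed above: 2 to 5 women expected in this position, a conception risk of 0.04% to 0.47% for each over the full gap, and 0.08% to 2.3% that at least one is affected. The absolute risk is small, and sample size, type I error and power are not touched. It is a gap in the safety schedule that should be closed because closing it is very cheap.

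**What to change.** In the Cohort B section, replace the test sentence with: a urine pregnancy test will be performed on the day of each research PSG, before dosing; a positive test means no dose. Apply it to all women of child-bearing potential, whatever their sequence, so that blinding is unaffected. This also states what follows a positive result, which the Cohort B steps do not say.

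The cost is one extra urine test per woman of child-bearing potential in Cohort B, 4 to 10 in all under the same assumption, at a visit that already takes place. Visits and analysis stay as they are.

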#### **Statistical Considerations:**

ANOVA and Fisher's Exact Test will be done to compare multiple means from repeated measures. A consultation with an expert statistician will also be considered for data analysis.

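### Cohort B is a randomised oxytocin/placebo crossover, but its stated comparison for all four outcomes is the diagnostic night against the oxytocin night, so the placebo night goes unused

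*Combined protocol and SAP*

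**What the plan says.** Cohort B, item 3, sets up the allocation: "Subjects will be randomized by the Investigational Drug Services Pharmacy of the MFA to be administered either Oxytocin (40 IU) or placebo". Item 5 then gives each subject whichever intervention was not received "during the first research PSG study within one hour prior to beginning the second polysomnography". Patient, technician and research staff are blinded. With the diagnostic study, each subject has three recordings: one undosed, one on oxytocin and one on placebo.

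Item 6 of the same section says the four outcomes will be "compared between the two sequential diagnostic PSGs (initial standard of care without oxytocin, and second for research with oxytocin) in the same subjects". The four are basal heart rate and mean heart-rate change with events (both primary), apnea-hypopnea index, and time in oxygen-saturation bands.

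Cohort A, item 4, uses nearly the same words: "initial without, and second with oxytocin) in the same subjects". Cohort A has only two nights and no placebo, so the sentence fits there.

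Three other places bear on the point:

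- Statistical Considerations names ANOVA and Fisher's exact test, which "will be done to compare multiple means from repeated measures". It names no contrast, period term or sequence term.
- The list of data to collect, after the exclusion criteria, begins: "The following information will be recorded on each patient before and after the use of intranasal oxytocin".
- Study Treatment places oxytocin or placebo "within 1 hour prior to sleeping during the second sleep study", whereas Cohort B has dosing before both research nights.

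**The concern.** The placebo night and the randomisation exist to separate the drug from everything else that differs between nights. Item 6 leaves both out. Its comparator differs from the oxytocin night in several ways besides drug:

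- It is undosed and open, so expectation is not balanced.
- It always comes first, so order and familiarity with the laboratory are not balanced.
- It may be up to 8 weeks earlier: up to 4 weeks to the first research night (item 2) and up to 4 more to the second (item 4).
- It may be a home test (item 1). Item 2 calls the research study "identical to the one they had for standard of care medical guidelines if they were diagnosed with OSA" in the laboratory, so that match does not extend to subjects diagnosed at home.
- It is the test on which the subject qualified, which matters most for the apnea-hypopnea index.

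If item 6 is followed, the sum of these differences enters the estimate for both primary outcomes. The Study Proposal section says the project is to supply preliminary data for larger trials, so a biased estimate would pass into their planning.

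**Working it through.** **Which nights are compared.** Let θ be the oxytocin effect, δ the non-drug shift from the diagnostic night to the first research night, and π the shift from the first research night to the second. Assume no carryover. Expected values relative to the diagnostic night:

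| Sequence | Diagnostic | Research 1 | Research 2 |
|---|---|---|---|
| Oxytocin first | 0 | δ + θ | δ + π |
| Placebo first | 0 | δ | δ + π + θ |

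*Item 6, oxytocin night minus diagnostic night.* The expected value is δ + θ in the first sequence and δ + π + θ in the second. With equal sequences the average is θ + δ + π/2, so the bias is δ + π/2.

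*Randomised contrast.* Research 1 minus research 2 has expectation θ − π in the first sequence and −θ − π in the second. Half the difference is [(θ − π) − (−θ − π)]/2 = θ. Both δ and π drop out.

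*A second reading of item 6.* If its later night means the second research PSG, that night is oxytocin only for subjects given placebo first. For the others it is the placebo night, so the sentence does not describe them.

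**Size.** The plan gives no figure to reproduce. From the documents: n = 40. Assumed: two-sided α = 0.05, 40 completers, 20 per sequence (the ratio is not stated), effects in SDs of the paired difference, equal SDs for the two paired differences, no carryover, and shifts of 0 to 0.5 SD.

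Paired t test: df = 39, critical value 2.023, noncentrality λ = d√40 with d the net standardised difference. Rejection probability = P(|T(39, λ)| > 2.023).

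| d | λ | Probability of rejection |
|---|---|---|
| 0 | 0 | 0.050 |
| 0.1 | 0.632 | 0.095 |
| 0.2 | 1.265 | 0.235 |
| 0.3 | 1.897 | 0.457 |
| 0.4 | 2.530 | 0.694 |
| 0.5 | 3.162 | 0.869 |

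*No drug effect (θ = 0, π = 0).* Here d = δ, so the table gives the false-positive rate of item 6 directly.

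*True effect 0.5 SD, opposing shift.* Shifts of 0.1, 0.2 and 0.3 leave d = 0.4, 0.3 and 0.2, so item 6 power falls from 0.869 to 0.694, 0.457 and 0.235.

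*Simulation of both analyses, no drug effect (20,000 trials per setting).*

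| δ | π | Item 6 rejects | Oxytocin vs placebo with period term rejects |
|---|---|---|---|
| 0 | 0 | 0.050 | 0.051 |
| 0 | 0.3 | 0.149 | 0.053 |
| 0.2 | 0 | 0.234 | 0.050 |
| 0.3 | 0 | 0.453 | 0.053 |
| 0.3 | 0.3 | 0.786 | 0.052 |
| 0.5 | 0 | 0.868 | 0.048 |

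The second row shows the π/2 term: a shift between the two research nights alone biases item 6 by 0.15 SD. In a separate run of 40,000 trials with θ = 0.5 and δ = −0.3, item 6 rejected 0.231 and the randomised contrast 0.870.

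**Cost of the period term.** Degrees of freedom go from 39 to 38. Power at 0.5 SD goes from 0.8694 to 0.8690, and the effect detectable with 80% power from 0.4543 to 0.4546 SD.

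**The case against.** The strongest reply is that item 6 is a drafting slip. It speaks of two nights where Cohort B has three, it nearly repeats Cohort A, and a blinded placebo makes little sense unless it is to be compared. A repeated-measures ANOVA of several means could also include the placebo night. This is probably how the sentence arose. It does not change what is written: item 6 is the only explicit comparison for Cohort B, and Statistical Considerations names none to set against it.

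Three narrower points stand in part:

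- Subjects qualify on an OSA diagnosis, not on heart rate. Regression to the mean therefore bears mainly on the apnea-hypopnea index, a secondary outcome. For the primary outcomes the argument rests on order, time, expectation and, for an unstated fraction, home versus laboratory recording.
- The percentages describe assumed shifts. With no shift, item 6 rejects 5% of the time, so they are not the trial's expected error rate.
- The 5% and 87% figures for the randomised contrast assume no carryover. The plan sets a maximum interval between research nights but no minimum, so the text does not secure that assumption.

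None of these favours the diagnostic night as the comparator when a randomised placebo night is available.

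**Conclusion.** The concern holds: item 6 is wrong as written for Cohort B. The stated comparison, covering both primary outcomes, omits the randomised control, and no other section supplies it. Its bias is δ + π/2, of unknown size and direction. As an illustration under the assumptions above, shifts of 0.2 to 0.5 SD would raise the false-positive rate from 5% to between 23% and 87%, and an opposing 0.3 SD shift would cut power for a 0.5 SD effect from 87% to 23%. That the comparison is confounded follows from the design alone and does not depend on these figures. An exploratory aim does not justify leaving out a control already being collected, so this must be fixed.

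**What to change.** Before unblinding:

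1. Replace the comparison in Cohort B, item 6, with wording such as: *For Cohort B, each of the four outcomes will be compared within subject between the oxytocin research PSG and the placebo research PSG.*
2. State the same contrast in Statistical Considerations, analysed in a within-subject model with treatment and period terms.
3. Use the Cohort B diagnostic PSG for eligibility and baseline description. If a contrast with that night is kept for comparability with Cohort A, label it supportive and non-randomised.
4. For Cohort B, align the before-and-after wording in the data list with the oxytocin and placebo nights.
5. Reconcile Study Treatment, which ties dosing to the second sleep study, with Cohort B items 3 and 5, which have dosing before both research nights.

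Items 1 and 2 cure the defect; the others bring the remaining text into line. The cost is a protocol amendment and minor extra analysis work, with no new visits, subjects or data. If the two paired differences have equal SDs, the loss of power is negligible: 86.9% at 0.5 SD either way.
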